## 5.0 Inclusion and Exclusion Criteria/ Study Population

Participants will complete a REDCap survey to be screened for eligibility. Inclusion criteria for usability testing (Aim 1), feasibility testing (Aim 2), and the subsequent pilot RCT (Aim 3) include: 1) current elevated depressive symptoms defined as a score of  $\geq 10$  (at least mild depression) on the Patient Health Questionnaire-8 (PHQ-8); if a participant reports a Beck Depression Inventory-II (BDI-II) score  $< 10$  during baseline the PHQ from screening will be repeated with the participant over the phone (64), 2) current smoking, defined as smoking 5+ cigarettes/day, for 25+ days out of the last 30, for the last 6+ months, 3) ownership of an Android or iOS smartphone compatible with Goal2Quit, 4) age 18+, 5) a

valid e-mail address that is checked daily to access follow-up assessments, 6) English fluency, and 7) has been seen by a primary care physician within the last year. Exclusion criteria include: 1) contraindications for NRT (pregnancy/intention to become pregnant/breastfeeding, recent cardiovascular trauma/uncontrolled hypertension), 2) severe visual impairment, which may limit ability to utilize an app, and 3) household member currently enrolled in the study.

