**Small-Scale RCT.** A two-arm RCT (N=150) will test the efficacy of Goal2Quit+NRT Sampling vs. TAU. See above for inclusion/exclusion criteria. After completing determination of eligibility, reviewing study procedures, completing informed consent, and completing baseline assessments, if eligible, the participant will be randomized 2:1 to either Goal2Quit + NRT sampling or TAU. Participants randomized to Goal2Quit + NRT sampling will be provided with their intervention in the same manner as feasibility testing participants. TAU participants will be mailed a package that includes only 1) NCI’s “Clearing the Air” booklet, which includes information on quitting smoking, and 2) Information on study participation, including the schedule of follow-up assessments and compensation. Participants will subsequently be emailed a REDCap link (accessible via smartphone, tablet, or computer) to complete follow-ups weekly for 8 weeks, with an additional follow-up at Week 12.

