### ***Quality Assurance***

Accuracy and completeness of the data collected will be ensured by weekly review. The REDCap system does not accept outliers, illogical response patterns, etc. The PI and research assistants will have weekly meetings to discuss any qualitative comments received during data collection and any problems in data collection. The PI will examine the database for potential irregularities monthly. Initial data analyses will examine distributions of variable scores and comparability of baseline characteristics across conditions (for Aim 3) in case analyses need to be adjusted for these. Confidentiality procedures are outlined above.

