### ***Trial Safety***

The potential risks and benefits and methods to minimize these risks are outlined in the “Risks to Subjects” section. AEs will be tracked and rated as mild, moderate or severe and as related to NRT by the participant. We will determine if any AEs result in dropouts, or are serious according to FDA guidelines. The PI ([name]) will serve as the Program Manager for AEs. All unexpected AEs will be monitored while they are active to determine if treatment is needed. Since a maximum two-week supply of OTC NRT will be provided, AEs will be rare. Nonetheless, they will be coded on a weekly basis using the FDA’s COSTART rules(82) and entered into a database. For each weekly study meeting, the research assistant(s) will prepare a summary of all AEs, including their severity, whether they caused a dropout, required treatment and presumed relation to drug intake. The PI will review this at the weekly study meeting (or before if more urgent). At the weekly meeting (or before if urgent), research assistants will report any premonitory symptoms to suggest emergence of a serious psychiatric condition (e.g., major depression, suicidality). See “Risks to Subjects” for procedures in place for handling significant clinical deterioration/suicidality. [name], a board-certified Family Medicine physician, will be available on ad-hoc basis for on-site medical supervision for any issues that cannot be resolved by Drs. [name] and [name].

Study procedures will follow as much as possible the FDA’s Good Clinical Practice Guidelines and our research team has found Spilker’s comprehensive text on conducting clinical trials to be useful(83). We will encourage, but not require, participants to notify their physicians that a) they are in a randomized controlled research study examining a treatment for mood and smoking cessation, and b) the physician should contact the PI directly if the physician has any questions.

The research assistants will be instructed not to reveal whether a person is a participant in the study and will report to the PI any outside requests for information about a participant or any breaches in confidentiality. All requests by participant’s physicians and other medical providers will be referred directly to the PI.

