## **13.0 Risks to Subjects**

This is considered a minimal risk study. Minimal risk means the probability and magnitude of harm or discomfort anticipated in the research are not greater in and of themselves other than those ordinarily encountered in daily life or during performance of routine physical or psychological examinations or tests. The potential risks in this study include those related to: a) clinical deterioration, b) suicidality, c) NRT, d) confidentiality, e) potential data breach from the app database, and f) frustration.

**a) Clinical deterioration:** Depressive symptoms will be monitored via the BDI-II. All participants will complete the BDI-II weekly online and at 12 weeks via a REDCap survey that is accessible via mobile phone, computer, and tablet web browsers. All participants will own an iOS- or Android-compatible smartphone. Thus, all participants will have access to the online BDI-II assessments. [name] and her research team will monitor participant BDI-II scores for possible clinical deterioration (i.e., increasing

depressive symptoms) throughout the course of the study as participants complete the BDI-II. Clinical deterioration will be defined as an increase of 10 or more points on the BDI-II from the baseline BDI-II assessment. In the event that a participant evidences clinical deterioration, [name] will contact the participant via phone and will provide referrals for local mental health resources and/or instruction to go to the ED or call 911 for immediate depression treatment. [name] will suggest that the participant seek treatment and then will follow-up with the participant via phone one week later. In the event that a participant evidences clinical deterioration, the participant will be allowed to continue in the trial, but we will recruit an additional participant for data collection purposes.

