**b) Suicidality:** [name] and her research team will monitor participant BDI-II scores for suicidality, defined as a response of “I would like to kill myself” or “I would kill myself if I had the chance” on the suicidal thoughts or wishes item of the BDI-II at any point during the study, including at baseline. In the event that a participant reports suicidal ideation, [name], a licensed clinical psychologist with 8 years of experience conducting risk assessments with high risk populations (e.g., adults in residential and outpatient substance use treatment, patients in a mood disorders clinic), will complete a risk assessment with the participant via phone. [name] will query the participant for details regarding the suicidal ideation, including a likelihood of harming oneself imminently and a plan for committing suicide. If the participant reports an imminent likelihood of harming him/herself or a plan for committing suicide, [name] will call emergency services and will remain on the phone with the participant until emergency services arrives. In the event that [name] makes contact with the participant (e.g., via phone), the participant expresses an imminent likelihood of harming him/herself, and the connection is lost, [name] will contact emergency services and will provide emergency services with the participant’s contact information, including address. In the event that the participant is not in imminent danger, [name] will provide referrals for local mental health resources and/or instruction to go to the ED or call 911 should suicidal ideation worsen. [name] will suggest that the participant seek treatment and then will follow-up with the participant via phone one week later. In the event that a participant endorses suicidal ideation but is not responsive to [name] phone call within 48 hours, [name] will e-mail the participant a list of local mental health resources and will suggest that the participant seek additional treatment. [name] will also ask that the participant respond to [name] either via phone or e-mail within 24 hours to confirm receipt of the treatment referrals. Should the participant not respond to [name] email within an additional 48 hours (4 days from completion of the assessment) **and** endorse “I would kill myself if I had the chance” on the BDI-II (score = 3 on BDI-II Item 9) [name] will call emergency services and provide emergency services with the participant’s name and address. In the event that a participant endorses suicidal ideation, the participant will be allowed to continue in the trial, but an additional participant will be recruited for data collection purposes.

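### Section 13.0 writes no step after the unanswered e-mail for an unreached participant who gives the lower of its two suicidality responses

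*Combined protocol and SAP*

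**What the plan says.** Section 13.0, item b, defines suicidality as either of two item 9 responses: a wish to kill oneself (here the lower response), or that one would do so given the chance (the higher response). The definition applies at every assessment, baseline included. Either response leads to a risk assessment by phone, carried out by a licensed psychologist.

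- **Reached by phone.** Emergency services are called if the participant reports an imminent likelihood of self-harm or a plan, whichever response was given. Otherwise the participant receives referrals and a follow-up call one week later.
- **Not reached within 48 hours.** An e-mail lists local resources and asks for an answer "either via phone or e-mail within 24 hours to confirm receipt of the treatment referrals".
- **No answer to the e-mail.** The limit is "within an additional 48 hours (4 days from completion of the assessment"). Emergency services are then called if, in addition, the higher response was given: "score = 3 on BDI-II Item 9". The word joining the two conditions is in bold.

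Item d of the same section and Protections Against Risk add that suitable action will be taken on suicidal intent or ideation, possibly including contact with the authorities. Neither sets a trigger or a time for a participant who does not respond.

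The BDI-II is given at baseline, after which RCT participants "complete follow-ups weekly for 8 weeks, with an additional follow-up at Week 12" (section 10.0).

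**The concern.** The protocol counts both responses as suicidality, and both lead to the call and the e-mail. After that only one of them leads anywhere. A participant who has stated a wish to die, and who answers neither phone nor e-mail, is asked to reply within 24 hours, and the text does not say what happens if no reply comes. Staff following the text would have no second call to make, no decision to record and no point at which to take the case up again.

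The situation is foreseeable. Everyone enrolled has a PHQ-8 of 10 or more, and surveys are completed remotely. The list in section 5.0 opens "Exclusion criteria include: 1) contraindications for NRT" and goes on to severe visual impairment and an enrolled household member; suicidal ideation is not on it. What is at stake is participant safety. No estimate of treatment effect is affected.

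**Working it through.** **1. The protocol's own figure.** Wait after the call plus wait after the e-mail: 48 h + 48 h = 96 h = 4 days. This agrees with section 13.0 when counted from completion of the assessment.

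**2. The two responses side by side (section 13.0, item b).**

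| Situation | Lower response | Higher response (score 3) |
|---|---|---|
| Reached, imminent risk or plan | Emergency services | Emergency services |
| Reached, not imminent | Referrals, call at one week | Referrals, call at one week |
| No answer by 48 h | E-mail, reply asked within 24 h | E-mail, reply asked within 24 h |
| No answer by 96 h | Nothing written | Emergency services |

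The one-week call does not fill the empty cell, because it is written for participants who were reached. The clinical-deterioration rule in item a (a rise of 10 or more BDI-II points from baseline) is a different trigger. It cannot operate at baseline, and it also relies on reaching the participant by phone.

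**3. Time to the next scheduled contact.** Assume surveys are completed when due and the e-mail goes out at 48 h (2 days).

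- Baseline to Week 7 (8 of the 10 time points): next BDI-II after 7 days, which is 7 − 2 = 5 days after the e-mail.
- Week 8: next BDI-II at Week 12, (12 − 8) × 7 = 28 days, which is 28 − 2 = 26 days after the e-mail.
- Week 12: none.

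These contacts are survey links. They help only if the participant completes the survey.

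**4. How many could be affected.** Ten BDI-IIs per RCT participant give 150 × 10 = 1,500 surveys, or 180 × 10 = 1,800 with the attrition allowance in section 11.0, if all are completed. The documents give no endorsement rate. Taking 0.5%, 1% and 2% per survey as assumptions:

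- 0.5%: 7.5 to 9 flagged surveys
- 1%: 15 to 18
- 2%: 30 to 36

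The gap applies only to the part of these with the lower response and no reply to either phone or e-mail:

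affected = flagged × share with the lower response × share of those not answering either

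The documents give neither share. At each assumed rate, the flagged count is therefore an upper limit, and the affected number itself is unknown.

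**5. Secondary point: the start of the path.** Let L be the time from survey completion to the first call. If the first 48 h runs from the call, the waits end at L + 96 h. That equals the stated 4 days only for L = 0; for L = 1 day it is 5 days. If both waits run from completion, the call must fall inside the first 48 h. Either way prompt review is implied, but no limit for item 9 review or first call is stated.

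**The case against.** The best defence is that the difference between the responses is deliberate. The bolded conjunction suggests that sending emergency services without the participant's agreement was reserved for the higher response, which is a reasonable graded choice. For the rest, Protections Against Risk has the psychologist act on suicidal ideation without requiring that the participant was reached. At 8 of 10 time points another BDI-II is due within a week, and few participants are likely to meet all the conditions.

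The first argument stands, and nothing here asks for automatic emergency services at the lower response. The others narrow the gap without closing it. The discretion carries no time and no record, and the weekly survey is missing for flags at Weeks 8 and 12.

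A reader might also infer that the 4-day limit hangs on the weekly study meeting, because Trial Safety says "At the weekly meeting (or before if urgent), research assistants will report any premonitory symptoms". The documents do not support this. The clock starts at completion of the assessment, and the psychologist and team watch the scores themselves. Item a describes BDI-II monitoring for deterioration "throughout the course of the study as participants complete the BDI-II". The sentence after the one on the weekly meeting refers suicidality to the Risks to Subjects section. The statement "The PI will examine the database for potential irregularities monthly" concerns data quality and is not the route for an item 9 response.

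Nor should section 15.0, which keeps study outcomes from the participant's physician, be read as barring any notice to others. Section 13.0, item d, makes suicidal intent a limit to confidentiality.

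**Conclusion.** The point holds in a narrow form. For an unreached participant with the lower response, section 13.0 writes no specific step after the e-mail. The next scheduled contact is 7 days after the flagged survey at baseline to Week 7, 28 days at Week 8, and absent at Week 12. These intervals follow from the assessment schedule and assume surveys completed when due. The number affected cannot be derived from the documents. The absence of a stated limit for item 9 review or first call is a lesser matter of missing detail.

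It would go too far to say that participants with the lower response are unprotected. They receive the call and the e-mail, and emergency services if they are reached and found to be at imminent risk. This is a cheap improvement to a safety procedure and does not invalidate the design.

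**What to change.** Amend section 13.0, item b, counting from survey completion:

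- **About 72 h (48 + 24), when the 24-hour reply request lapses:** a second call for either response.
- **96 h:** keep emergency services for score 3. For the lower response, require a documented decision by the study psychologist: a further call, a welfare check, or no further step with the reason.
- **7 days:** one more call if a flagged Week 8 or Week 12 survey has had no response, since no survey falls due that week.
- **Optional:** state that item 9 is reviewed and the first call made within the existing 48 h window, for example through a REDCap alert. Neither a fixed 24 h limit nor a weekend delegate is needed.

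The cost is a few lines of text, a protocol amendment, and at most two required extra calls per unanswered flagged survey. At the assumed rates, all flagged surveys together come to 7.5 / 22 = 0.3 to 36 / 22 = 1.6 per month over the 22-month enrollment period, and only the unanswered ones need extra calls. Some participants may not welcome more contact, which is one reason to leave the 96 h step for the lower response to clinical judgement.

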
**c) NRT:** Through brochures delivered as part of the sampling intervention, participants will be educated about lozenge/patch adverse events (AEs) and nicotine intoxication symptoms. We will clearly advise against use of NRT during pregnancy and breast-feeding but we will not require pregnancy tests to be in the study. Female participants will be required to sign a waiver endorsing that: 1) they are not pregnant, 2) they do not plan on becoming pregnant during the study period, and 3) they are using an accepted birth control method. We will not explicitly encourage or discourage use of combined medication (patch+lozenge), though accompanying brochures will advise smokers not to smoke while using NRT product (even though most studies have demonstrated no significant events for combined use). The sampling experience is meant to provide smokers with a real-world opportunity to “test drive” different medications. Our accompanying brochures will discuss the anticipated negative consequences of dual use (nausea, headache) and advise participants to discontinue one or both products should they arise. Participants will be provided with our study phone number and instructed to call our study personnel should they experience such AEs or if they have questions/concerns about NRT use. Given

the 2-week sampling experience, we expect AEs, which will be assessed across follow-up timepoints via REDCap, to be rare and mild. In a prior trial, our group found that 9% of participants who utilized NRT samples in an attempt to quit reported an AE(84). None of these AEs were unexpected, nor did any study participants drop out as a result of an NRT-related AE. Participants will be encouraged to contact [name] as soon as possible for serious AEs and for those conditions that OTC labeling suggests seeing a provider. We will withdraw participants who have a serious AE. For other AEs, if the participant wishes it, the participant will be withdrawn from the study.

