**f) Frustration:** Participants may become frustrated while completing questionnaires or while using Goal2Quit. Participants will be informed that they may refuse to answer any question(s) that they do not wish to answer and that they may discontinue use of Goal2Quit at any time (which will be tracked as a study outcome).

Since patients will all currently be receiving medical care at MUSC, there are no additional risks associated with participation in this study.

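### Withdrawal after a serious adverse event would probably also end that person's BDI-II safety checks and later outcomes; the plan should say that the surveys continue (minor)

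*Combined protocol and SAP*

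**What the plan says.** All references are to the combined protocol and SAP.

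- **The rule.** Section 13.0 c) (NRT): "We will withdraw participants who have a serious AE". It does not say from what. The following sentence does, for lesser events: "For other AEs, if the participant wishes it, the participant will be withdrawn from the study".
- **What the surveys carry.** Section 13.0 a) has staff watch BDI-II scores for deterioration "throughout the course of the study as participants complete the BDI-II". Section 13.0 b) detects suicidality from one item of the same questionnaire. Section 13.0 c) says of AEs, "which will be assessed across follow-up timepoints via REDCap".
- **Schedule.** Section 10.0 sets nine remote follow-ups, at Weeks 1 to 8 and Week 12, of about 20 minutes each. The only AE row in the schedule table concerns NRT.
- **What continues after a serious AE.** Section 12.0 (Regulatory Issues) has serious AEs reported within 48 hours and their follow-up reported. Section 12.0 (Trial Safety) has unexpected AEs monitored while they are active, with a family physician available when needed.
- **Neighbouring rules.** For side effects of using patch and lozenge together, the brochures "advise participants to discontinue one or both products should they arise", with no mention of leaving the study. Section 13.0 f) lets app use stop at any time and records this as an outcome. For clinical deterioration, "the participant will be allowed to continue in the trial, but we will recruit an additional participant for data collection purposes"; the rule for suicidal ideation is similar.
- **Analysis.** Section 11.0 plans hierarchical linear modeling (HLM) on all available data, 100 active and 50 control participants, and quit-attempt rates of 40% and 15%.

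**The concern.** The natural reading of the rule, taken with the sentence after it, is withdrawal from the study. If staff apply it that way, they have no instruction to keep sending the surveys.

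Two things are then lost. First, the person's scheduled deterioration and suicidality checks end just after a serious health event, in a sample selected for elevated depressive symptoms (PHQ-8 of at least 10, Section 5.0). Second, that person's later BDI-II and smoking outcomes are missing for a health-related reason, although the surveys are remote and already scheduled.

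The scope is also unclear. The sentence stands in the NRT subsection, so it may cover only NRT-related events, which would fall in the active arm. It may equally cover serious AEs of any cause in both arms. Neither reading settles whether the surveys continue.

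**Working it through.** **Figures in the plan.** The plan gives no serious-AE rate and no estimate of this loss, so there is no figure to reproduce. The nearest number is the ceiling of 5% for significant AEs in Section 12.0 (Regulatory Issues). The monitoring report described later in Section 12.0 lists significant and serious AEs separately, so 5% serves here only as an upper case.

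**Inputs from the plan.** Nine follow-ups; 100 active and 50 control; attempt rates 40% and 15%; $10 per survey and two $20 bonuses.

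**Assumptions.** Serious-AE rates of 1% and 2%; withdrawal after Week 2; a constant hazard of a first quit attempt over 12 weeks. The plan labels 40% and 15% as point prevalence; they are treated here as 12-week cumulative rates. Attempts reported before withdrawal count, and later unreported attempts are scored as none.

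**Step 1: checks lost per person.** After Week 2, 9 − 2 = 7 BDI-II checks remain, so 7/9 = 78% are lost. The range by timing is 1 to 9 of 9.

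**Step 2: surveys lost.**
- NRT-related reading, 1 or 2 of 100 active participants: 7/900 = 0.8% or 14/900 = 1.6% of active-arm surveys.
- All-cause reading, 1% or 2% of 150, which is 1.5 or 3 people: 10.5/1,350 = 0.8% or 21/1,350 = 1.6% of all surveys.

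**Step 3: chance that a withdrawn person's first attempt goes unrecorded.**
- Active: 0.40 − (1 − 0.60^(2/12)) = 0.40 − 0.082 = 0.318
- Control: 0.15 − (1 − 0.85^(2/12)) = 0.15 − 0.027 = 0.123

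**Step 4: effect on the attempt rates.** With k active participants withdrawn of 100, the active rate is 40 − 0.318k. With rate r in both arms, the difference is 25 − 100r(0.318 − 0.123). The extreme case supposes that every withdrawn active participant would have made a first attempt afterwards, so the active rate is 40 − k.

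| Rate | Active rate, NRT-related reading | Extreme case | Difference, all-cause reading |
|---|---|---|---|
| 1% (k = 1) | 39.7% | 39% | 24.8 points |
| 2% (k = 2) | 39.4% | 38% | 24.6 points |
| 5% (k = 5) | 38.4% | 35% | 24.0 points |

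For k = 1, withdrawal after Week 1, 4 or 8 shifts the active rate by −0.36, −0.24 or −0.11 points, against −0.32 after Week 2.

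**Step 5: yardstick.** The standard error of the difference is √(0.40×0.60/100 + 0.15×0.85/50) = √(0.0024 + 0.00255) = 0.070. The 95% half-width is 1.96 × 0.070 = 0.138, or 13.8 points.

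**Step 6: dropping withdrawn people instead.** If they are excluded rather than scored as non-attempters, and all or none of them were attempters, the active rate is 39/99 to 40/99 (39.4% to 40.4%) at 1%. At 5% it is 35/95 to 40/95 (36.8% to 42.1%). If those lost were 10 BDI-II points worse, which is the plan's deterioration threshold, the active-arm mean would shift by 0.1 points at 1% and 0.5 points at 5%.

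**The case against.** **The survey stop is inferred.** No sentence says that surveys end. The rule itself does not name what is stopped, and the consent form, which is not in the documents, may deal with follow-up after withdrawal. This stands: what is shown is an unclear instruction whose natural reading ends the surveys.

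**The person is not left unattended.** A serious AE is reported quickly and followed up, the PI reviews AEs weekly, a physician can be consulted, and patients stay in usual care. A reader might infer that monitoring ceases altogether, and the documents contradict that. But these provisions concern the event. None is a scheduled check of mood and suicidal thoughts.

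**The plan does not consistently separate stopping treatment from leaving the study.** A reader might take the deterioration and suicidality rules as proof that it does. They are not: those participants stop nothing and simply remain. Only the brochure advice and the app rule offer some support for the distinction.

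**The effect is trivial and already allowed for.** Section 11.0 assumes 20% attrition and will examine dropout, and in the team's prior trial no one left for this reason: "nor did any study participants drop out as a result of an NRT-related AE". This stands for the estimates and is why the point is minor.

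**Compulsory withdrawal is cautious.** True for NRT, and a stop rule should stay. Caution about a nicotine product does not require ending a questionnaire.

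**Conclusion.** The point holds as a minor, cheap improvement. Following the rule as written would probably end BDI-II safety checks and outcome collection for anyone with a serious AE. Withdrawal after Week 2 would cost that person 7 of 9 checks.

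A reader might conclude that the effect-size estimate is at risk of bias. The documents do not support that. At 1% to 2% the shifts are 0.2 to 0.6 points in the main calculation and at most 2 points in the extreme case. At 5% they are 1.0 to 1.6 points, or 5 points if all five people would have gone on to a first attempt. All lie well inside a half-width of 13.8 points. HLM keeps the data collected before withdrawal and would not score missing surveys as no attempt, so the real shift is probably smaller. Any imbalance between arms is also an inference: it arises mainly if the rule covers only NRT-related events.

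The conclusion rests on reading the rule as study withdrawal (likely, not certain) and on the assumed rates, timing and constant hazard. The reason to change the sentence is to keep the person's monitoring and remove an ambiguity, not to protect power or precision.

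**What to change.** Replace the sentence in Section 13.0 c) with:

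> After a serious AE, the participant stops study NRT (active arm) unless the PI, with the study physician, considers the event unrelated. In both arms, the weekly and Week 12 surveys and BDI-II monitoring continue unless the participant declines further data collection.

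Offer the same surveys-only option to those who stop for other AEs, with full withdrawal remaining their choice. This wording keeps the protective stop, names who decides on exceptions, and also covers TAU participants, who receive no study NRT.

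**Cost.** One or two sentences in an amendment and a matching line in the consent form. Sample size and analysis do not change. Each person receives a few more 20-minute surveys. For withdrawal after Week 2, payments are at most 7 × $10 + $20 + $20 = $110 per person, or $220 for two people. The drawback is some added burden on someone who has just been ill, which the right to decline limits.
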